2.5.3 Handling of missing values/censoring/discontinuations

No imputation will be performed for missing data for the primary endpoint.

2.5.4 Supportive and sensitivity analyses

1. The non-parametric Mann-Whitney-Wilcoxon test will be carried out as a sensitivity analysis due to the potential non-normality of the CFU data.
2. The primary efficacy analysis will be repeated in the PPS as a supportive analysis.

2.6 Analysis of secondary and exploratory efficacy objective(s)

For efficacy analysis, patients assigned to placebo arms will be pooled across the 3 cohorts, as the number of placebo capsules is not expected to impact the efficacy assessments. Unless otherwise specified, the following analysis will be conducted both over the treatment epoch (through Day 113) and over the entire study period (through Day 169).

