3.2 Rationale for study design

The patient population will be described in more detail in the [Section 4](#) below.

This study is designed to find a dose and regimen [REDACTED] in non-CF BE patients with pulmonary *P. aeruginosa* infections. A parallel study design with three treatment cohorts is used to investigate three different TIP doses and regimens versus placebo.

The study will implement a within-cohort blinding approach. If the study were blinded across all arms, all of the subjects in the study would need to inhale the maximal dose of 10 capsules every day to maintain the blind in a double-blind double dummy design (5 morning + 5 evening). In previous double-blind studies in CF patients (EVOLVE and EDIT) it has been noted that tolerability of placebo was overall similar with that of TIP, being most likely driven by the amount of powder inhaled and its oro-pharyngeal deposition ([Konstan et al 2011a](#), [Konstan et al 2011b](#)). In order to assess tolerability (defined by the rate of local AEs) related to the dose, within-cohort blinding is planned in this study. For each dose level, the patients will be randomized as follows: TIP:TIP/placebo cyclical: placebo in a 2:2:1 ratio. This randomization scheme will allow the analysis of tolerability across treatment arms within the same cohort for those patients on active study drug without bias from an open design, and will also permit comparison of efficacy outcomes to a pooled placebo group. The randomization scheme has been chosen to ensure that a total of 36 patients are randomized into the three cohorts to receive placebo (12 placebo patients per cohort) and also the number of patients between TIP/placebo cyclical and TIP are evenly distributed 24 patients per treatment arm. It

is not expected that the amount of placebo powder administered will influence efficacy measurements, therefore the placebo patients will be pooled (12 patients per dose, in total 36 patients on placebo for the efficacy endpoint). Patients from both TIP and TIP/placebo cyclical treatment arms will be pooled within the same cohort for the primary endpoint measurement at Day 29, as they both receive the same active treatment during the first 28 days. For further details about the analysis, see [Section 9.4](#).

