3.4 Rationale for choice of comparator

Placebo is chosen as comparator since no approved active comparator is available for the indication under study. It is considered necessary to include placebo in order to determine which doses and frequency of regimen offer an efficacy benefit in terms of reduction of bacterial load. Both patients and investigators remain blinded to the assignment to active or placebo within the cohort. The subjects would be aware of the number of capsules and the frequency of daily administration of active and placebo that they have been assigned to but have no knowledge of whether they were allocated to active or placebo.

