9.7 Sample size calculation

Sample size estimation was based on a difference of $2.0 \log_{10} \text{CFU/g}$, with standard deviations of $2.0 \log_{10} \text{CFU/g}$. The assumptions were based on conservative estimates from published results ([Konstan et al 2011a](#), [Konstan et al 2011b](#), [Barker et al 2000](#), and [Wilson et al 2013](#)). As there are three primary comparisons between the three doses versus placebo, the Bonferroni multiplicity adjustment has been used (0.05/3) for sample size calculation. Using $\alpha=1.67\%$ (two-sided) and 90% power, the sample size estimation yielded $n = 36$ subjects per treatment group as valid for ITT analyses. This takes into account an approximate 20%-discontinuation rate. For the primary efficacy analysis, patients from TIP continuous and TIP cyclical regimen within the same cohort will be pooled as they receive exactly the same treatment during the first 28 days. Placebo patients will be pooled across the 3 cohorts, as the number of placebo capsules is not expected to influence the change in *P. aeruginosa* bacterial counts. With the current study design, the power is 94% to detect a reduction of $2.0 \log_{10} \text{CFU/g}$ for each dose level versus placebo.

For calculation of sample size, NQuery Advisor version 7.0 module MTTO-1 was used.

10 Ethical considerations

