2.6.3 Statistical hypothesis, model, and method of analysis

In general, unless otherwise specified, the following 6 pairwise comparisons will be performed for the secondary endpoints at the 5% significance level without multiplicity adjustment, wherever an inferential analysis is specified:

- TIP 3 capsules OD versus pooled placebo
- TIP/placebo cyclical 3 capsules OD versus pooled placebo
- TIP 5 capsules OD versus pooled placebo
- TIP/placebo cyclical 5 capsules OD versus pooled placebo
- TIP 4 capsules BID versus pooled placebo
- TIP/placebo cyclical 4 capsules BID versus pooled placebo

Descriptive summary statistics by cohort, treatment arm, pooled treatment arm by regimen and pooled placebo will be provided where applicable.

In addition, data will also be summarized for selected endpoints, by pooling continuous TIP regimens together (i.e. TIP 3 capsules OD. from Cohort A + TIP 5 capsules OD from Cohort B+ TIP 4 capsules BID from cohort C) and pooling cyclic TIP regimens together (i.e. TIP/placebo cyclical 3 capsules OD from Cohort A + TIP/placebo cyclical 5 capsules OD. from Cohort B+ TIP/placebo 4 capsules BID cyclical from cohort C) vs pooled placebo.

In addition, the following 2 pairwise comparisons will be performed for the selected endpoints at the 5% significance level without multiplicity adjustment:

- Pooled TIP continuous regimens versus pooled placebo
- Pooled TIP/placebo cyclical regimens versus pooled placebo.

Forest plot will be plotted for below endpoints in addition to the primary endpoint for each treatment arm across 3 cohorts compared with pooled placebo separately and also for the comparison between pooled TIP continuous (pooled from 3 cohorts) with pooled placebo and for

the comparison between pooled TIP/placebo cyclic (pooled from 3 cohorts) with pooled placebo.

- LS Mean difference in log₁₀ CFUs of *P. aeruginosa* in sputum and CI
- For exposure adjusted rate and CI of pulmonary exacerbations during the study
- For incident rate ratio and CI for anti-pseudomonal antibiotics during the study
- Incident rate ratio and CI hospitalization due to serious respiratory-related AEs across the entire study period
- LS Mean difference in QoL-B RSS and CI

2.6.3.1 *P. aeruginosa* colony forming units (CFU)

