2.10 Patient reported outcomes

Quality of Life Questionnaire-Bronchiectasis (QoL- B)

QoL-B is assessed at Visit 2 (Baseline), Visit 102 (Day 8), Visit 103 (Day 29), Visit 104 (Day 57), Visit 105 (Day 85), Visit 106 or TD (Day 113), Follow-up Visit 201 (Day 141) and Follow-up Visit 202 or PSD (Day 169).

The QoL-B consists of 37 items across 8 domains: Physical, Role Functioning, Vitality, Emotional Function, Social Functioning, Treatment Burden, Health Perception and Respiratory Symptoms. Each of the 37 items is scored from 1 to 4.

Items in the questionnaire are expressed either 'negatively' or 'positively', therefore a number of items must be recorded before the scores for each of the domains are calculated. The score is calculated by adding the score obtained for each item of a domain (scale), after any necessary recoding. Scoring for each domain can be computed only if at least half the items have been completed. If not, then the domain should not be scored and should be considered missing for that particular person who filled out the questionnaire.

[figure not shown]
[figure not shown]
Descriptive statistics will be provided for each domain score for all applicable visits for the FAS by treatment arm [and](#) pooled arms by continuous and cyclic regimens. Changes from baseline to each post-baseline visit will also be summarized. For the QoL-B Respiratory Symptom Score (RSS), further summaries will be provided for:

- Patients with/without pulmonary exacerbations during the treatment period
- Patients with overall study drug compliance $\geq 80\%$

The change from baseline in QoL-B RSS will be analyzed using a linear repeated measure model. The model will contain treatment, baseline macrolide use, visit (visits 102 to 202), and treatment-by-visit interaction as fixed effects with baseline QoL-B RSS, baseline-by-visit interaction as covariates. The within-patient correlation will be modeled using the unstructured covariance matrix in the mixed model. If the model does not converge, then the compound symmetry covariance structure will be used. The restricted maximum likelihood method will be used.

QoL-B correlation with other patient reported outcome measures will be performed by RTI health solutions; consequently these are not detailed within this SAP.

Details on deriving the domain scores can be found in [Section 5.5](#).

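### Six single-arm contrasts on QOL-B respiratory symptoms (and, less directly, exacerbations) use placebo pooled over 3, 5 and 8 capsules a day, mixing drug effect with powder load and known cohort; cohort could be kept in the pooled-regimen models at almost no cost

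*SAP*

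**What the plan says.** SAP 2.6 introduces all secondary efficacy analyses with the rule that "placebo arms will be pooled across the 3 cohorts, as the number of placebo capsules is not expected to impact the efficacy assessments". Protocol 9.5.1 has the same rule, and Protocol 3.2 and the opening of Protocol 9 also pool placebo for efficacy.

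SAP 2.6.3 then sets six comparisons of a single dose-and-regimen arm with pooled placebo, without multiplicity adjustment. For selected endpoints it adds two comparisons across cohorts: "Pooled TIP continuous regimens versus pooled placebo" and the cyclical counterpart. Both sets are to be shown in forest plots for QOL-B RSS and exacerbation rate.

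None of the models concerned has a cohort term. For RSS (SAP 2.10), "The model will contain treatment, baseline macrolide use, visit (visits 102 to 202), and treatment-by-visit interaction as fixed effects", with baseline RSS and its interaction with visit as covariates. The exacerbation models in SAP 2.6.3.2 likewise omit cohort. Amendment 3 gives confounding with treatment as the reason.

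Other parts of the protocol bear on the pooling assumption:

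- Protocol 3.2 reports that in cystic fibrosis studies "tolerability of placebo was overall similar with that of TIP, being most likely driven by the amount of powder inhaled" and its deposition in the throat.
- Protocol 3.4 says of the blinding: "The subjects would be aware of the number of capsules and the frequency of daily administration".
- Protocol 9 does not pool placebo for safety. SAP 2.7 shows it by cohort as well as pooled.

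**The concern.** For bacterial counts it is reasonable to expect that the number of placebo capsules does not matter. For symptoms, the documents offer no data for that expectation, and their own tolerability rationale points the other way. SAP Table 1-1 lists cough and bronchospasm as local adverse events, and RSS items ask about cough, wheeze and breathlessness. The same symptom is thus reported by cohort as an adverse event, but compared with pooled placebo as a patient-reported outcome.

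Blinding holds only within a cohort. By design, two thirds of the comparator for any single arm comes from other cohorts, whose patients know that they take a different number of capsules or take them at a different frequency. Protocol 3.2 justifies the design by comparison within a cohort, and the single-arm contrasts give part of that protection up.

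The trial is meant to guide the choice of dose and frequency. A shift that differs by cohort changes how the six arms appear relative to one another, and no planned inferential analysis tests the pooling assumption. SAP 2.5.4 plans only a rank test and a per-protocol repeat, both for bacterial counts.

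**Working it through.** **The plan's own figure.** Protocol 9.7: "Sample size estimation was based on a difference of" 2.0 log10 CFU/g, SD 2.0, two-sided alpha 0.05/3. "This takes into account an approximate 20%-discontinuation rate".

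- Evaluable: 48 × 0.8 = 38.4 active per dose and 36 × 0.8 = 28.8 pooled placebo.
- SE = 2 × sqrt(1/28.8 + 1/38.4) = 0.493, so 2/0.493 = 4.06. Power is 95.2% (normal) or 94.2% (noncentral t), against the stated 94%.
- At 90% power, 28 (normal) or 29 (t) per group, divided by 0.8, gives 35 to 36.25, against the stated 36.

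The sizing reproduces. It concerns bacterial counts and says nothing about symptom outcomes.

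**Load difference from pooled placebo.** Capsules per day are 3, 5 and 8 (SAP 2.4.1). Capsules per session are 3, 5 and 4 (Protocol 5.2). Allocation is 1:1:1 across cohorts and 2:2:1 within each, so the pooled placebo mean weights cohorts equally:

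- per day: (3 + 5 + 8)/3 = 5.33
- per session: (3 + 5 + 4)/3 = 4

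Let RSS fall by b points per extra capsule (assumption; higher RSS is better). Bias = b × (pooled placebo load − arm load):

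| Load measure | A | B | C |
|---|---|---|---|
| Per day | +2.33b | +0.33b | -2.67b |
| Per session | +1b | -1b | 0 |

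With b = 0.5 to 1.5 (assumption), daily load gives +1.2 to +3.5 for A and -1.3 to -4.0 for C. Session load gives +0.5 to +1.5 for A and -0.5 to -1.5 for B. Protocol 6.4.6 gives a minimal important difference of 8.

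**Effect on tests (daily load, no drug effect, N = 107).** Assume an RSS SD of 12 to 20. If 8 capsules cost 4 points relative to 3, a cohort C arm is declared different at nominal 5% in 6.1% to 8.2% of trials. If they cost 8 points, the figure is 9.6% to 18.0%. By session load, cohort C has no bias.

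**Exacerbations (daily load, log-linear).** Assume a rate ratio for 8 versus 3 capsules of 1.10, 1.25 or 1.50. With no drug effect, the apparent rate ratio versus pooled placebo is 0.96, 0.90 or 0.82 for A and 1.05, 1.12 or 1.22 for C.

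**Is cohort confounded with treatment?**

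- Pooled-regimen models (continuous, cyclical, placebo): every treatment occurs in every cohort. Treatment plus cohort has rank 5 (1 + 2 + 2), so the two are fully crossed. All three groups have the same expected capsule mix, so the pooling bias is 0.
- Seven-level treatment (six active arms plus placebo): adding cohort gives rank 9 on 9 cells. Cohort is estimable through the placebo arms, and each contrast becomes arm versus own-cohort placebo.

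**Precision at N = 107 (SD units).**

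- Pooled regimen, no cohort: sqrt(1/42.8 + 1/21.4) = 0.265.
- Pooled regimen, average of three within-cohort differences: sqrt((1/14.27 + 1/7.13)/3) = 0.265. No loss at balance.
- Single arm versus pooled placebo: sqrt(1/14.27 + 1/21.4) = 0.342.
- Single arm versus own-cohort placebo: sqrt(1/14.27 + 1/7.13) = 0.459. The ratio is 1.34.
- With SD 12 to 20, the 95% half-width of the own-cohort contrast is 1.96 × 0.459 × SD, about 11 to 18 points.

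**The case against.** The strongest reply is about the estimand. Powder comes with the regimen, so if more capsules worsen symptoms, that is a real cost. A common comparator keeps this cost in the ranking of regimens, whereas own-cohort placebo subtracts it. This stands as a reason to keep the planned contrasts. It does not make them drug effects, and it does not deal with expectation from known assignment.

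The symptom link is partial. Protocol 3.2 speaks of tolerability as local adverse events and names no individual symptoms there. The cough, dyspnoea and wheeze cited in the protocol come from nebulised solution. At Visits 201 and 202 no powder is inhaled, so only carry-over and expectation could act. For exacerbations the link is weaker still: Protocol 6.4.4 requires at least three of six findings and a decision that antibiotics are needed.

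Much is already shown descriptively by cohort and arm (SAP 2.6.1.2 and 2.6.3.2), and SAP 1 labels all inference exploratory after closure at 107 of 180 patients. That label answers small numbers, not a directional shift. Own-cohort contrasts rest on about 14 versus 7 patients and could not confirm a bias of the sizes above. This also stands, and limits them to a display.

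**Conclusion.** The point holds for the six single-arm contrasts on RSS and, less directly, on exacerbations: as planned, they cannot separate drug effect from powder load and known cohort. The amount is unknown. Every figure above depends on an assumed slope, on linearity and on the load measure. The one feature common to both load measures is that the 3-capsule arms are favoured.

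A reader might infer four stronger things that the documents do not support:

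- **That the SAP widened the pooling beyond the protocol.** Protocol 3.2, 9 and 9.5.1 already apply it to efficacy generally.
- **That the pooled-regimen contrasts are biased.** Under the common 2:2:1 ratio they are not, apart from chance or dropout imbalance.
- **That the highest daily dose is necessarily penalised.** This follows from daily load. By session load the 5-capsule arms are penalised and cohort C is not.
- **That a gap of 2.5 to 7.5 points between lowest and highest dose is to be expected.** That is 5b with b = 0.5 to 1.5 by daily load, and neither b nor the load measure is given.

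For the pooled-regimen contrasts, the finding is that the stated reason for dropping cohort does not apply, because cohort is a level of the randomisation and is crossed with treatment.

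**What to change.** 1. Add cohort as a factor to the pooled-continuous and pooled-cyclical versus placebo models: the RSS mixed model, the negative binomial models and the ANCOVA. In the Cox models use it as a covariate, or as a stratum if events permit, since crossing it with macrolide use makes six strata for about 21 placebo patients. State that treatment has three levels in these models; the SAP does not say how the pooled contrasts are to be fitted. They then rest on blinded within-cohort comparisons and are protected from chance and dropout imbalance. The cost is 2 degrees of freedom, with no loss of standard error at balance.

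2. For QOL-B RSS, and secondarily for exacerbations, show each TIP arm against its own-cohort placebo with its confidence interval beside the planned pooled-placebo contrast. Label it as a descriptive sensitivity display with a standard error about 34% larger.

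All planned contrasts stay and no new data are needed. Because the protocol's current RSS and exacerbation models also omit cohort, the change should be recorded in SAP section 4. At the same time, reconcile the protocol summary (primary model) and Protocol 9.5.1.3, which still list cohort despite Amendment 3.

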2.6.1 Secondary endpoints

2.6.1.1 *P. aeruginosa* colony forming units (CFU)

Anti-microbial efficacy of TIP versus placebo over the entire study duration, as measured by the absolute change in log₁₀ CFUs of *P. aeruginosa* in sputum from baseline to each post-baseline visit (Visits 102 (Day 8), 103 (Day 29), 104 (Day 57), 105 (Day 85) and 106 (Day 113)), will be assessed by morphotype and sum of all morphotypes (mucoid, dry, small colony-variants). For patients with a negative *P. aeruginosa* result, i.e, NPAI, the quantitative test result for the analysis will be imputed for each morphotype with log (99) as this represents the detection level for a dilution of 100. Means together with the 95% CIs will be graphically displayed over time. The summaries will be provided by treatment groups Cohort A: TIP, Cohort A: TIP/placebo cyclical, Cohort B: TIP, Cohort B: TIP/placebo cyclical, Cohort C: TIP, Cohort C: TIP/placebo cyclical, Pooled TIP and Pooled TIP/placebo cyclical and pooled placebo. Comparisons between treatment regimens across all cohorts versus pooled placebo will also be analyzed.

The number and percentage for patients with no *P. aeruginosa* in sputum and number and percentage of patients with a positive result of *P. aeruginosa* in sputum will be tabulated by cohort, treatment arm, pooled arms by continuous and cyclic regimens and visit. Percentages will be based on the number of patients for whom microbiology results exist per visit.

The number and percentage of patients with NPAI at 2 consecutive post-baseline visits will also be presented by cohort and treatment arm, pooled arms by continuous and cyclic regimens.

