2.5.1 Primary efficacy endpoint

The primary efficacy variable is the absolute change in the bacterial load in sputum as assessed by the change in log₁₀ CFUs of *P. aeruginosa* from baseline to Day 29 of treatment. The specimens with more than 1 bacterial morphotype, the sum of all bacterial morphotype will be used to calculate change from baseline values.

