2.5.2 Statistical hypothesis, model, and method of analysis

The comparisons of 3 doses of active treatment (TIP 3 capsules OD, 5 capsules OD, and 4 capsules BID) versus pooled placebo will be evaluated by testing the following null hypothesis (H₀) versus the alternative hypothesis (H_a):

H₀: TIP treatment arm is equal to pooled placebo group in bacterial load in sputum at Day 29

H_a: TIP treatment arm is not equal to pooled placebo group in bacterial load in sputum at Day 29

The primary efficacy endpoint will be analyzed using the analysis of covariance (ANCOVA) model. The model will contain treatment, baseline CFU (in log₁₀ unit), and baseline macrolide use (yes/no). The adjusted means will be displayed together with the associated standard error and 2-sided 95% CI. Pairwise comparisons of TIP dosing groups will be conducted versus placebo. To control the family-wise type-I error rate (3 dose levels vs. placebo) at the 2-sided 5% significance level, the step-wise Dunnett procedure will be used.

For the primary efficacy analysis, patients from treatment arms TIP and TIP/placebo cyclical regimen will be pooled for each cohort. This is possible because all patients within the same cohort on the TIP treatment arms (cyclical or continuous) are receiving the same treatment during the first 28 days. Placebo patients will be pooled across the 3 cohorts, as the number of placebo capsules is not expected to influence the change in *P. aeruginosa* bacterial counts.

The estimated adjusted treatment difference (TIP – placebo) will be displayed along with the associated standard error, 2-sided 95% CI, and p-value (2-sided).

The estimated treatment difference and CI will be displayed in forest plot for the treatment arms TIP and TIP/placebo cyclical regimen pooled for each cohort vs pooled placebo across 3 cohorts.

For other efficacy analyses up to and including Day 29, patients from treatment arms TIP and TIP/placebo cyclical regimen will be pooled for each cohort; placebo patients will be pooled across the 3 cohorts.

If no *P. aeruginosa* isolated (NPAI) are detected, i.e, no growth detected, at a given visit where the laboratory sample was available at that visit, the value will be imputed as 99 based on the lower limit of detection (dilution factor is currently 1/100). Log 10(99) will be used in the analysis.

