The primary efficacy parameter (CFU) will be analyzed using a similar ANCOVA model as used in primary efficacy analysis at Day 85, Day 113 and Day 169. The model will contain treatment, baseline CFU (in log₁₀ unit), and baseline macrolide use (yes/no).

The analysis will not be performed by the subgroup of morphotypes. Six pairwise comparisons will be evaluated as specified in [Section 2.6.3](#). The estimated adjusted treatment difference for each of the 6 comparisons (TIP–placebo) will be displayed along with the associated standard error, 2-sided 95% CI. In addition, CFU data will be summarized by morphotype and sum of all morphotypes at each scheduled visit.

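### The SAP sets a culture-negative sample to 99 CFU once in the primary rule but to log(99) per morphotype in the secondary rule, and does not bar summing the imputed values

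*SAP*

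**What the plan says.** **Primary rule.** SAP 2.5.1 defines the endpoint as change in log10 CFU. Where a specimen has more than one morphotype, "the sum of all bacterial morphotype will be used to calculate change from baseline values". SAP 2.5.2 then deals with samples that were available but grew no P. aeruginosa: "the value will be imputed as 99 based on the lower limit of detection (dilution factor is currently 1/100"), followed by "Log 10(99) will be used in the analysis". That is one value per sample, with the log base stated.

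**Secondary rule.** SAP 2.6.1.1 covers Visits 102 to 106 (Days 8, 29, 57, 85 and 113). The change in log10 CFU "will be assessed by morphotype and sum of all morphotypes (mucoid, dry, small colony-variants"). For a negative result, "the quantitative test result for the analysis will be imputed for each morphotype with log (99"), and the reason given is "as this represents the detection level for a dilution of 100". No log base is attached to this constant. The section goes on to plots of means with 95% CIs over time, summaries by arm and pooled regimen, and comparisons of regimens with pooled placebo.

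**Later-visit analysis.** SAP 2.6.3.1 applies a similar ANCOVA to the primary CFU parameter at Days 85, 113 and 169, not by morphotype. It adds: "In addition, CFU data will be summarized by morphotype and sum of all morphotypes at each scheduled visit".

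**The concern.** Two rules are written for the same culture-negative sample. The first fixes its total at 99 CFU. The second fixes each morphotype at 99 and places the morphotype sum beside it, without saying whether imputation comes before or after summing. Because SAP 2.6.1.1 includes Visit 103 (Day 29), one specimen could carry two different totals at the primary time point.

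The choice of 99 has a purpose: it puts a negative just below the smallest count that the assay can report. A total built from several imputed values loses that property. It raises the floor for negatives while leaving positives where they are. If cultures turn negative more often on TIP than on placebo, the raised floor works against TIP, and most in the arms and visits with most clearance. In a dose- and regimen-finding study, the plots of CFU over time by regimen will be read closely, so this is worth settling before programming.

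**Working it through.** **Inputs**
- Primary value for a negative sample: 99 CFU, log10 (SAP 2.5.2).
- Secondary value for a negative sample: log(99) per morphotype, for negative results only (SAP 2.6.1.1). It is taken as log10 because the variable in the same paragraph is log10 CFU.
- Number of named morphotypes: 3 (SAP 2.6.1.1).
- Detection level: dilution of 100, so one colony counts as 100 CFU (SAP 2.5.2 and 2.6.1.1).
- Planning difference and SD: 2.0 and 2.0 log10 CFU/g (SAP 3), used only as a yardstick.
- Share of negatives on active: 20-40%. Protocol 1.1 reports eradication from under 20% up to 40% in nebulised tobramycin pilot studies, with 35% in the double-blind one. Using this for TIP is an assumption.
- Share of negatives on placebo: 0-10%, an assumption with no figure in the documents.

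**Step 1. Reproduce the plan's constant.** The smallest positive is 1 x 100 = 100 CFU, log10 = 2.000. One unit below is 99, log10(99) = 1.996. The primary rule therefore ranks every negative just below every positive.

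**Step 2. Apply the secondary rule literally and sum on the CFU scale.** 3 x 99 = 297, log10(297) = 2.473. The excess over the primary rule is 2.473 - 1.996 = log10(3) = 0.477 per negative sample.

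**Step 3. Check the ordering.** A single-morphotype positive of one colony is 2.000 and of two colonies (200 CFU) is 2.301. Both fall below 2.473. Three colonies (300 CFU) give 2.477, which is above it. So positives of 100 to 296 CFU are overtaken. With only two morphotypes imputed the total is 198 (2.297), still above one colony.

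The inversion arises because the text limits imputation to negative samples. If the absent morphotypes of a one-colony positive were also set to 99, its total would be 100 + 99 + 99 = 298 (2.474), and the order would just be kept. The SAP does not provide for that.

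**Step 4. Effect on the TIP-placebo difference.** Assume baseline samples are positive, so the shift enters only the post-baseline value, and positives are unchanged. Then:

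shrinkage = (share negative on active - share negative on placebo) x 0.477

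| Negative on active | 0% on placebo | 10% on placebo |
|---|---|---|
| 20% | 0.20 x 0.477 = 0.095 | 0.10 x 0.477 = 0.048 |
| 35% | 0.35 x 0.477 = 0.167 | 0.25 x 0.477 = 0.119 |
| 40% | 0.40 x 0.477 = 0.191 | 0.30 x 0.477 = 0.143 |

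The range is about 0.05 to 0.19 log10. The largest value is 0.191 / 2.0 = 0.096 of the planning SD.

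**Step 5. Set the total once.** With log10(99) assigned to the total of a negative sample, every negative is 1.996 at every visit. That is below the lowest positive (2.000) and identical in the primary and secondary outputs.

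**The case against.** The strongest reply is that the SAP never instructs anyone to add imputed values. SAP 2.6.1.1 names two kinds of output, by morphotype and summed, and then gives a per-morphotype constant. The explicit summing rule in SAP 2.5.1 is for specimens with more than one morphotype, and a negative specimen has none. The rule in SAP 2.5.2 is worded for any visit with an available sample, so it can be read as governing the total everywhere, with 2.6.1.1 serving only the by-morphotype displays. A careful programmer could reach the right answer.

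This stands in part. It shows that the fault is an inconsistent and open specification, not a certain numerical error. It does not remove the conflict. SAP 2.5.2 sits under the primary analysis, SAP 2.6.1.1 gives its own rule for the same samples in the paragraph that introduces the sum, and nothing says which prevails for the total.

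The reply also limits the reach of the point. SAP 2.6.3.1 analyses the primary CFU parameter with a similar model, which more naturally inherits the definitions in 2.5.1 and 2.5.2. The planned comparisons are against pooled placebo, so any effect on dose-to-dose reading is indirect. SAP 1 already describes all inference as exploratory after early closure.

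**Conclusion.** The point holds as a conflict between two stated rules. Followed literally, SAP 2.6.1.1 raises a negative sample by 0.48 log10 over the primary rule and ranks it above positives of 100 to 296 CFU. The exposed outputs are the secondary sum-of-morphotypes summaries, plots and regimen comparisons. The Day 85, 113 and 169 ANCOVA is affected only if it is run on that total.

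The likely shrinkage of the TIP-placebo difference, 0.05 to 0.19 log10, is modest against the planned 2.0. It rests on the assumed 20-40% negatives on active and 0-10% on placebo, and on positive baselines. The shift is against TIP only if negatives are more frequent on TIP. The active range comes from a different formulation and may not fit later visits: Day 113 follows a placebo period in the cyclical arms, and Day 169 is off treatment in all arms.

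A reader might infer three stronger things that the documents do not support:
- **The primary result is biased.** It is not: SAP 2.5.2 gives one value and the base, and that analysis is unaffected.
- **The unlabelled log is a natural log.** The variable in the same paragraph is log10 CFU, and 2.5.2 writes the same constant in base 10. The missing base is an omission to tidy, not a plausible source of error.
- **The later-visit ANCOVA is already wrong.** The text does not settle that it uses the summed total, and the more natural reading is that it does not.

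**What to change.** Amend SAP 2.6.1.1 to say three things:
1. The constant is log10(99).
2. The total for a culture-negative sample is set once to log10(99), at every visit and in both primary and secondary analyses.
3. Per-morphotype log10(99) is used only in by-morphotype displays and is never summed.

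A cross-reference from SAP 2.6.3.1 to the same rule would settle which total the later-visit ANCOVA uses. The cost is one or two sentences and a line in the programming specification. No new data are needed, and the primary analysis does not change.
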